# **Statistical Analysis**

Statistical analysis would be used estimate the proportion of slides falling above or below the specified threshold. Covariates for smear result, "LBC system" and relevant data from the survey of practice would be included as covariates in logistic random effects model of the proportion falling either side of the specified threshold. This analysis would be carried out using each laboratory's current threshold and that derived in part 2 of the study.

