# HTA brief, part 1: to survey which thresholds are used in current practice at laboratories using LBC and the reasons for their choice of threshold

The first part of the study surveys current working practice to establish both the declared formal laboratory thresholds for LBC specimen adequacy and the active thresholds which are operating in practice, with a view to determining the respective levels of each and whether they are different.

It also establishes cohorts of inadequate, negative and abnormal cases which have been reported in a routine screening setting for which total cell counts are known. This information will supplement that from part 2 and will provide an estimate of screening sensitivity at different levels of cellularity.

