# **Outcome Measures**

Outcome would indicate how closely laboratories achieve declared criteria and levels derived by part 2. Statistical modelling may give some indications of practices (SOPs) that are more successful.

HTA brief, part 2: to establish a threshold of adequacy by carrying out multiple analyses from individual samples to ascertain the number of cells necessary to ensure that samples cannot be wrongly labelled 'negative' when they are inadequate.

The total number and relative proportion of dyskaryotic cells compared with normal squamous cells in a cervical sample will influence the probability of their reliable detection. In a case control study of women with CIN3 who wrongly received negative reports, the number of abnormal cells was the strongest differentiating factor. Mitchell and Medley reported that where there were less than 50 abnormal cells on the slide, the odds of a false negative report being issued was 23.7 times greater than when there were 200 or more abnormal cells . However, cell size , staining characteristics and pattern of presentation will also influence detection rates .

Many of the current defining publications on the effect of cellularity on the detection of cervical disease, including the Mitchell and Medley paper, are based on conventional spread cytology not on LBC samples. Further, most studies use the Bethesda Terminology System which has traditionally accepted as adequate, samples of lower cellularity than would be accepted under current UK guidance . However, limited work on LBC samples would suggest that similar criteria for disease detection may apply. Bolick has shown that optimal detection rates for HSIL (high-grade squamous

intraepithelial lesion) and LSIL (low-grade squamous intraepithelial lesion) are achieved when sample cellularity is greater than 20,000 well visualised squamous cells .

In this part of the study, these variables will be assessed by producing serial dilutions of known cases of varying morphological type and by producing preparations with varying ratios of dyskaryotic to total squamous cells but with a similar background cellularity.

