# **Summary of Project:**

The first part of the study surveys current working practice to establish both the declared laboratory thresholds for LBC specimen adequacy and those thresholds which are operating in practice, with a view to determining the respective levels of each and whether they are different.

It also establishes cohorts of inadequate, negative and abnormal cases which have been reported in a routine screening setting for which total cell counts are known. This information will supplement that from part 2 and will provide an estimate of screening sensitivity at different levels of cellularity.

The second part of the study will assess the contribution of differing total cellularity; relative proportion of abnormal: normal cells; and dyskaryotic sub-type on the likelihood that the slide will be categorised as abnormal. Slide sets comprising serial dilutions of known abnormal cases and of preparations with varying ratios of dyskaryotic to total squamous cells will be assessed by independent review panels. The results will allow an estimate of a level of cellularity at which most abnormalities are likely to be detected and will provide an evidence base to inform national guidance relating to the minimum acceptable cellularity for a cervical LBC sample.

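### Part 1 promises the level of the active adequacy threshold, but its stated analysis yields only proportions either side of a supplied cut and never estimates that level in cells

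*Protocol*

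**What the plan says.** The Protocol, under HTA brief, part 1, sets the declared laboratory thresholds beside "the active thresholds which are operating in practice, with a view to determining the respective levels of each and whether they are different". The Summary of Project repeats the aim: "those thresholds which are operating in practice, with a view to determining the respective levels of each and whether they are different".

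The declared level comes from the questionnaire and the laboratory's operating procedure (Laboratory Practice Survey). For the slides, the Part 1 Statistical Analysis section begins "Statistical analysis would be used estimate the proportion of slides falling above or below the specified threshold". It then specifies a "logistic random effects model of the proportion falling either side of the specified threshold", with smear result, LBC system and survey data as covariates. On the choice of cut it says "This analysis would be carried out using each laboratory's current threshold and that derived in part 2 of the study".

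The Part 1 Outcome Measures section matches the analysis: "Outcome would indicate how closely laboratories achieve declared criteria and levels derived by part 2". The Part 1 Sample Size section gives precision for two such proportions (inadequates above the cut, negatives below it) and power for a trend in low cellularity across report types. It also says that the inadequate slides will be used to describe the distribution of cellularity in that group.

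**The concern.** The aim names a quantity in cells: the level at which practice switches from inadequate to negative. In the stated model the response is the side of a cut on which a slide falls, and both cuts are inputs. One is what the laboratory declares and the other comes from Part 2, so neither is estimated from the Part 1 slides. No section says how the counts of inadequate and negative slides become an active threshold, or how its level is set against the declared one.

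At stake is one of the two headline results of Part 1. Followed as written, the study could report how often slides fall on the wrong side of the declared cut, but not what threshold laboratories actually work to, although the count and report category of every slide will be held.

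**Working it through.** **1. What the planned figures measure.** Part 1 Sample Size gives 1,120 inadequates (56 × 20) with 5% above the cut, and 2,800 negatives (56 × 50) with 1% below it. The half-width is 1.96 × √[p(1 − p)/n].

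- Inadequates: 1.96 × √(0.05 × 0.95/1,120) = 1.28% (stated 1.3%).
- Negatives: 1.96 × √(0.01 × 0.99/2,800) = 0.37% (stated 0.4%).

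Both figures reproduce, treating slides as independent. Both are precisions of pooled shares at a fixed cut. For one laboratory the same rates imply 20 × 0.05 = 1 inadequate and 50 × 0.01 = 0.5 negatives beyond the cut, with nominal half-widths of about 9.6 and 2.8 percentage points.

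**2. Whether the proportion can stand in for the level.** The protocol gives no cell-count distribution, so this step uses assumed values: log-normal counts with median M and log-SD 0.8, declared threshold D = 15,000, and a sharp switch at active threshold T below D. Every slide below T is then inadequate, so no inadequate lies above D. The share of negatives below D is [F(D) − F(T)] / [1 − F(T)], where F(x) = Φ[ln(x/M)/0.8].

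| T | M | F(D) | F(T) | Negatives below D |
|---|---|---|---|---|
| 5,000 | 60,000 | 0.0416 | 0.0009 | 4.1% |
| 12,400 | 40,000 | 0.1101 | 0.0716 | 4.1% |
| 5,000 | 40,000 | 0.1101 | 0.0047 | 10.6% |
| 8,000 | 40,000 | 0.1101 | 0.0221 | 9.0% |

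The first two rows give the same planned output for active thresholds that differ 2.5-fold (12,400/5,000). In the last two rows the distribution is held fixed, and thresholds of 5,000 and 8,000 differ by about 5.3 against 4.5 slides of 50.

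**3. What a direct estimate must allow for.** A logistic model of inadequate v negative on log count gives the level directly, but slides are sampled by report at 20:50. Take the routine inadequate rate r as 1% to 2% (Summary in Plain English) and assume 90% of reports are negative. The log odds of inadequate are then inflated by ln[(20/50)/(r/0.9)]:

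- r = 1%: ln(0.4/0.0111) = ln 36 = 3.58.
- r = 2%: ln(0.4/0.0222) = ln 18 = 2.89.

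Without an offset, the count at which the two reports are equally likely is too high by the factor exp(inflation/slope). With assumed slopes of 2 to 5 per log unit, the extremes are exp(3.58/2) = 6.0 and exp(2.89/5) = 1.8. This is a property of the added model and the reason it needs an offset. It is not an error in the present plan.

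**The case against.** The strongest reply is that Part 1 is mainly about adherence. Relevance to Commissioning Brief promises evidence on how closely laboratories follow their local guidelines, Outcome Measures says the same, and the Objectives list asks for the cellularity of samples by report type rather than an active threshold for each laboratory. The analysis serves those commitments. The distribution of counts in inadequate slides also bears on where practice separates the categories. The analysis text is a short outline that excludes nothing further, and an unseen analysis plan might add the estimate.

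Much of this stands. A reader might infer that the planned proportions cannot tell a laboratory working just under its declared threshold from one working far under it. The document does not support that, because it also plans the negatives below the cut. With M = 40,000 and log-SD 0.8, active thresholds of 14,000 and 8,000 against a declared 15,000 give 1.7% and 9.0% of negatives below it. The question of whether the thresholds differ is therefore partly served. A reader might also take the aim to require a separate estimate for each laboratory. In the text the word each refers to the declared and the active thresholds, so that is a reasonable reading but not the literal one.

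The level itself is still missing. The protocol fixes the response, the cuts and the outcome, and an analysis plan that followed them faithfully would not estimate an active level even pooled over laboratories. The distribution in inadequates alone does not locate the switch to negative.

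**Conclusion.** The concern holds as a mismatch between a stated aim and the stated analysis. The proportions can reveal departure from the declared threshold, and the pooled adherence results are unaffected. What is missing is an estimate of the active level in cells and its comparison with the declared level. That these sections state no such estimate can be read directly from the protocol. The size illustration, in which identical output arises from active thresholds 2.5-fold apart, rests on an assumed log-normal distribution and a sharp switch. It shows that the level is not identified from the proportions, and does not predict what the study would find. This is a worthwhile, inexpensive improvement rather than a fault that invalidates Part 1.

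**What to change.** Add to the Part 1 Statistical Analysis section:

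- A logistic mixed model of report (inadequate v negative) on log cell count, with a laboratory random intercept and LBC system as covariate. Include a random slope only if the data support it; 20 inadequates and 50 negatives per laboratory may not.
- An offset for the 20:50 quotas, from each laboratory's KC61 or equivalent LBC-only rates, which the questionnaire already requests.
- The active threshold, defined as the count at which inadequate and negative are equally likely. Report it overall, by LBC system and as shrunken laboratory estimates, and compare it with the declared threshold on the log scale.
- A rule that repeat preparations from one case are handled as one case, because the Slide Survey files them under the issued report whatever the individual slide shows.

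Add the comparison to the Part 1 Outcome Measures. If the estimate is not wanted, withdraw the promise of levels from HTA brief, part 1 and from the Summary of Project.

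The cost is analysis work only, with no new slides or readings. The results will depend on a fitted curve and on rates that may cover less than 12 months in some laboratories, and estimates for single laboratories will be imprecise. A sensitivity analysis over plausible inadequate rates would show how far the offset matters. It matters less where the switch is sharp: at slopes of 10 to 20 the factor in the working falls to about 1.2 to 1.4.

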# **Outcome Measures**

Outcome would indicate how closely laboratories achieve declared criteria and levels derived by part 2. Statistical modelling may give some indications of practices (SOPs) that are more successful.

HTA brief, part 2: to establish a threshold of adequacy by carrying out multiple analyses from individual samples to ascertain the number of cells necessary to ensure that samples cannot be wrongly labelled 'negative' when they are inadequate.

The total number and relative proportion of dyskaryotic cells compared with normal squamous cells in a cervical sample will influence the probability of their reliable detection. In a case control study of women with CIN3 who wrongly received negative reports, the number of abnormal cells was the strongest differentiating factor. Mitchell and Medley reported that where there were less than 50 abnormal cells on the slide, the odds of a false negative report being issued was 23.7 times greater than when there were 200 or more abnormal cells . However, cell size , staining characteristics and pattern of presentation will also influence detection rates .

Many of the current defining publications on the effect of cellularity on the detection of cervical disease, including the Mitchell and Medley paper, are based on conventional spread cytology not on LBC samples. Further, most studies use the Bethesda Terminology System which has traditionally accepted as adequate, samples of lower cellularity than would be accepted under current UK guidance . However, limited work on LBC samples would suggest that similar criteria for disease detection may apply. Bolick has shown that optimal detection rates for HSIL (high-grade squamous

intraepithelial lesion) and LSIL (low-grade squamous intraepithelial lesion) are achieved when sample cellularity is greater than 20,000 well visualised squamous cells .

In this part of the study, these variables will be assessed by producing serial dilutions of known cases of varying morphological type and by producing preparations with varying ratios of dyskaryotic to total squamous cells but with a similar background cellularity.

### Design:

Given the operating characteristics of the two LBC systems the dilutions must be made using different techniques. In SurePath  $^{\text{TM}}$ , the slide preparation directly reflects the content of the sample. A poorly cellular sample will have a poorly cellular slide preparation. Serial dilutions can therefore be made according to standard methodologies. ThinPrep $^{\text{@}}$  is a filtration based system in which the fluid sample is repeatedly 'sipped' through the filter until a specific level of electrical impedance is reached. Hence in some samples most, if not all, of the specimen may be filtered to reach a system pre-determined adequacy level. In others, only a tiny fraction of the total specimen will be filtered. The cell yield on the slide does not therefore match the cellularity of the original sample. In order to produce serial dilutions of Thin Prep $^{\text{@}}$  samples, the machine must be offered highly dilute samples in which all of the available cellular material will be filtered. Increasingly cellular samples can be produced by adding increasing aliquots of a known sample to specimen vials containing only Preserveyt $^{\text{@}}$  fluid.

A total of 180 SurePath™ and 180 Thin Prep® cases will be selected from material routinely accessioned at the Royal Liverpool University Hospital and the Manchester Cytology Centre, which display a range of histologically confirmed low and high grade cytological abnormalities. Following selection, the cases will be entered on the study database and anonymised to ensure compliance with the Human Tissue Act 2004. The cases will range from those containing plentiful hyperchromatic (darkly staining) dyskaryotic cells, to those which have scanty abnormal cells; are pale staining; show minimal nuclear changes or form microbiopsy fragments. The latter sub-types are known to cause diagnostic problems.

Eight preparations will be made from each sample. Serial dilutions with approximate cellularities of 5-10k, 10-15k, 15-20k, 20-25k, 25-35k, 35-45k, 45-55k and 55+k will be made from half of the cases. The range of dilutions is skewed towards preparations of lower cellularity as these are expected to have higher false negative rates. The remaining cases will be mixed with known negative cases in varying proportion to establish sets of slides containing <25, 25-49, 50-99, 100-149, 150-199, 200-399, 400-799, 800-1600 and 1600+abnormal cells. In total 3,000 new slides will be prepared.

Each of the prepared slides will be assessed by two members of a four panel expert cytology group (to include [name]). Each slide will have a total cell count and a total abnormal cell count performed by the two panel members. Cases in which there is a variation of >10% between either of these counts will be assessed by at least three panel members on a multi-headed discussion microscope and a consensus decision reached.

The prepared slides will then be block randomised with 1,000 negative and 1,000 inadequate cases (total of 2,000) of similar cellularities in a ratio of 3:2 to minimise screener outcome bias.

Determination of "true" negative is always a problematic area in cervical cytology. In order to address this the Team proposes a modification to the existing protocol whereby 200 of the 1,000 negative slides will derive from confirmed HPV-ve cases. 100 of these HPV-ve slides will be acquired from archived material from the ARTISTIC/MCM trial. As the ARTISTIC/MCM trial used only Thin Prep® cases, these will be matched by newly acquired HPV-ve material from the SurePath™ system. It is estimated that 150 HPV tests will be required to obtain a cohort of HPV-ve, Cytology-ve cases.

A total of 5,000 slides will thus be gathered in this part of the study. Sets of 100 slides will then be established and recorded in a pre-determined database as for the first part of the study. A database will again be provided to each participating laboratory as an individualised floppy disc / CD. Each disc will contain details of the anonymised slide sets allocated to that laboratory and will allow direct entry of the morphological assessment for each slide. Laboratories will be asked to screen each slide once under routine primary screening conditions and to assess each slide as either inadequate, negative, low or high-grade dyskaryosis. Approximately 18-20 groups each of three laboratories will be established

to form 'mini' slide circulations. Each slide will therefore be subject to three independent reviews; however, the membership of each group will be withheld to avoid contamination of results. Approximately 15,000 slide-assessments will be performed in this arm of the study. The morphological assessments will be entered on the pre-formatted discs and returned with the slide sets to the Study Centre.

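### Part 2 allocation does not keep the eight preparations from one case apart, so a laboratory may read sibling slides; a case-level constraint would prevent this at almost no cost

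*Protocol*

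**What the plan says.** All references are to the protocol, Part 2.

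- **Slides.** Under Design, 180 SurePath and 180 ThinPrep cases are selected and "Eight preparations will be made from each sample". Half of the cases form a dilution series over total cellularity, from 5-10k upward ("45-55k and 55+k will be made from half of the cases"). For the other half, "The remaining cases will be mixed with known negative cases in varying proportion"; the introduction to Part 2 describes these as having "varying ratios of dyskaryotic to total squamous cells but with a similar background cellularity". Siblings therefore differ in total cellularity in the dilution half and in number of abnormal cells in the mixing half. The stated total is: "In total 3,000 new slides will be prepared".
- **Allocation.** The prepared slides are block randomised with 1,000 negative and 1,000 inadequate slides "in a ratio of 3:2 to minimise screener outcome bias". Sets of 100 are formed and circulated among about 18-20 groups of three laboratories. Each laboratory screens each slide once.
- **Safeguards.** Slides are anonymised, and "the membership of each group will be withheld to avoid contamination of results".
- **Matching.** The Sample Size section notes that slides are matched across bands, but only as a possible gain in power.
- **Model.** The Statistical Analysis section specifies a logistic random effects model with random terms for slide and source. It names none for reading laboratory.

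**The concern.** The safeguards address other risks. The 3:2 mix stops screeners from guessing that most slides are abnormal. Withheld membership limits contact between laboratories. Anonymised labels hide the identifier but not the cells. None of them stops one laboratory from receiving two or more preparations of the same sample.

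A screener who has called a richly cellular slide abnormal, and then recognises the same material on a sparse slide, may call the sparse one abnormal too. Misses are expected mainly at low cellularity, so this carry-over would act mostly there (or, in the mixing half, at low abnormal-cell number). It would flatten the pick-up curve and lower the estimated minimum cellularity, which is the less safe direction for a study meant to set a minimum. The planned model has no term that could detect or remove the effect, and the allocation cannot be repaired once slides have been read.

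**Working it through.** **Inputs from the protocol.** Eight preparations per case, so seven siblings per slide; 360 cases; 3,000 prepared slides among 5,000; g = 18-20 groups; pick-up of 95% v 80%; 90 slides per band; kappa 0.75. (360 x 8 = 2,880; using this instead of 3,000 makes no material difference below.)

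**The plan's own figure.** For 95% v 80% at 80% power, with two-sided alpha 0.05 (assumed; none is stated), the requirement is 76 slides per band without and 88 with continuity correction, close to the stated 90. Corrected power at 90 is 81%. With three reads the design effect is 1 + 2 x 0.75 = 2.5, the effective number is 90 x 3 / 2.5 = 108, and corrected power is 88.5%, near the stated 87%. The sample size reproduces and is not affected by this point.

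**Load per laboratory.** 5,000/20 to 5,000/18 = 250-278 slides, of which 60%, or 150-167, are prepared slides.

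**Sharing a group with at least one sibling.** Under unconstrained allocation, P = 1 - (1 - 1/g)^7.

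| Groups available to a case | P |
|---|---|
| 18 | 33.0% |
| 20 | 30.2% |
| 9 (split by system, assumed) | 56.2% |
| 10 (split by system, assumed) | 52.2% |

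Sampling without replacement gives 32.7%, 30.0%, 55.9% and 52.0%. All three laboratories of a group read the same slides, so sharing a group means sharing all three.

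**How many cases per laboratory.** The number of a case's slides in a given group is about Binomial(8, 1/g). P(two or more) is 0.0691 at g = 18 and 0.0573 at g = 20. Multiplied by 360, this is about 21-25 cases per group. Three or more occurs for only about 2-3 cases.

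**Richer sibling read first, lowest band.** All seven siblings are richer. If K of them are in the same group and reading order is random, the sparse slide is not first with probability K/(K+1). Averaging over K ~ Binomial(7, p) with p = 1/g gives 1 - [1 - (1 - p)^8]/(8p).

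- g = 18: 1 - 0.3670/0.4444 = 17.4%
- g = 20: 1 - 0.3366/0.4000 = 15.9%
- g = 9: 1 - 0.6103/0.8889 = 31.3%
- g = 10: 1 - 0.5695/0.8000 = 28.8%

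If two screeners split a laboratory's slides equally (assumed), p is halved and the figure for 18-20 groups falls to about 8-9%. In higher bands fewer siblings are richer, so the figure is smaller.

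**Effect on a true 80% pick-up.** Observed = 80% + 20% x r x s, where s is the share read after a richer sibling and r is the proportion of misses turned into hits. The protocol gives no value for r; 10-30% is assumed.

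- 18-20 groups: 80 + 20 x 0.10 x 0.159 = 80.3% to 80 + 20 x 0.30 x 0.174 = 81.0%
- Split by system: 80 + 20 x 0.10 x 0.288 = 80.6% to 80 + 20 x 0.30 x 0.313 = 81.9%

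**The case against.** The strongest reply is that recognition is nowhere shown. Slides are anonymised, mixed with negative and inadequate slides of similar cellularity, and read as in routine screening among 250 or more others, possibly by several people. This stands: the bias is a possibility of unknown size. The Design section does include pale, scanty and microbiopsy presentations, but it describes them as diagnostically difficult, not as easy to recognise again.

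The direction is not certain either. A sparse slide read first as negative or inadequate could carry over to a richer sibling. Upward bias at the sparse end is the more likely result because that is where misses are expected, but it is not assured.

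A reader might also infer that laboratories would often receive several slides from one case, or that a case's slides might stay together and push 80% to as much as 86%. Neither is supported. Two or more slides from a case would reach a given group for only about 21-25 of 360 cases, and nothing in the text suggests blocking by case.

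Finally, it can be said that separation is an allocation detail the statistician could add, since Part 2 sets are recorded in the way used for Part 1, where the statistician fixes the order. The protocol does not rule this out. But the balanced design described for Part 1 under Cell Counting balances originating laboratory and cytological type, not case, so repeating it would not separate siblings.

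**Conclusion.** The point holds as a weakness of the allocation, not as a demonstrated bias. The protocol states how prepared slides are randomised, and that scheme leaves 30-33% of them sharing their reading laboratories with a sibling, or 52-56% if circulations are split by system. The share that matters for priming in the lowest band is about 16-17% (29-31% if split), and lower with several screeners per laboratory.

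On the assumed 10-30% conversion of misses, the shift is about 0.3-1.0 percentage points, or up to about 2 if split by system, against a planned contrast of 15 points. These figures rest on random allocation, random reading order, one screener per laboratory and an assumed recognition effect. The conclusion that readers will recognise siblings and that low-cellularity pick-up is inflated goes further than the document allows. The case for acting is that the safeguard is cheap, the possible error is probably in the less safe direction, and it cannot be corrected after circulation.

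**What to change.** Add one sentence to the Part 2 Design: the eight preparations of a case go to eight different laboratory groups, with cellularity bands (dilution half) or abnormal-cell bands (mixing half) rotated so that each group reads every band about equally often. Same-laboratory exposure to siblings then falls to zero. Eighteen to 20 groups are enough, as are 9-10 per system. In the dilution half, 180 cases over 18-20 groups give about 9-10 slides per band per group. The Design lists nine abnormal-cell bands for eight preparations, so in the mixing half the rotation should be defined on the bands actually made.

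The cost is a constraint in the allocation program. Slides per band, three reads per slide and about 15,000 assessments are unchanged. The downside is that comparisons between bands within a case run entirely across laboratories. Most already would: under random allocation only 1/20 to 1/18 (5-6%) of sibling pairs fall in the same group. A reading-laboratory term should therefore be added to the Part 2 model alongside slide and source.

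### Part 2 makes eight preparations per case but lists nine abnormal-cell bands with no rule for the missing one, and the stated 3,000 prepared slides follows from neither number.

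*Protocol*

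**What the plan says.** All of this is in the protocol, under HTA brief part 2.

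- **Cases** (Design): "A total of 180 SurePath ™ and 180 Thin Prep ® cases will be selected", so 360 in all.
- **Preparations** (Design): "Eight preparations will be made from each sample".
- **Cellularity series** (Design): dilutions with "approximate cellularities of 5-10k, 10-15k, 15-20k, 20-25k, 25-35k, 35-45k, 45-55k and 55+k" "will be made from half of the cases". That is eight bands for 180 cases.
- **Abnormal-cell series** (Design): the remaining 180 cases are mixed with known negatives "to establish sets of slides containing <25, 25-49, 50-99, 100-149, 150-199, 200-399, 400-799, 800-1600 and 1600+abnormal cells". That is nine bands.
- **Totals** (Design): "In total 3,000 new slides will be prepared". To these are added 1,000 negative and 1,000 inadequate slides at 3:2, and then "A total of 5,000 slides will thus be gathered in this part of the study". Three reviews of each slide give about 15,000 assessments.
- **Sample Size**: 1,440 slides for each system, plus a further 960 cases of similar cellularity. The section does not say whether the 960 is per system or overall.

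**The concern.** The number of preparations per case and the number of bands should agree if each case is to run through its series. They agree for total cellularity and disagree for abnormal-cell number. The protocol does not say which band a case leaves out, or how omissions are spread over cases.

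The second series exists to study abnormal-cell number, which the part 2 introduction reports, from one case-control study, as the strongest factor separating false negative reports. The Design section deliberately mixes cases with plentiful abnormal cells and cases with scanty, pale or otherwise difficult ones. If laboratory staff choose the omitted band according to what a case can supply, the bands could end up holding different mixes of case type. Part of any difference in pick-up between bands could then reflect case difficulty.

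Separately, the prepared-slide total drives the filler slides, the circulation sets and the reading workload, and the document gives two figures for it that do not agree.

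**Working it through.** **Inputs.** 360 cases (180 per system), 8 preparations per case, half of the cases in each series, 8 cellularity bands, 9 abnormal-cell bands, 2,000 filler slides and 3 readings per slide, all from Design; 1,440 slides per system and 960 further cases, from Sample Size. I assume that the half split is made within each system, giving 90 cases per system in each series.

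**Reproducing the plan's figures.**
- Sample Size: 180 x 8 = 1,440 per system, and 2 x 1,440 = 2,880. This reproduces exactly.
- Design, prepared slides: 360 x 8 = 2,880, which is 120 (4.0%) below the stated 3,000. With nine preparations in the abnormal-cell series only, 180 x 8 + 180 x 9 = 1,440 + 1,620 = 3,060, which is 60 (2.0%) above. With nine throughout, 360 x 9 = 3,240 (8.0% above). Since 3,000 / 360 = 8.33, no single whole number of preparations per case gives 3,000.
- Once 3,000 is accepted, the rest follows: 3,000 + 2,000 = 5,000; 3,000:2,000 = 3:2; 5,000 x 3 = 15,000. So the discrepancy enters at the 3,000.

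**Empty cells in the abnormal-cell series.**
- Nine bands for 180 cases: 180 x 9 = 1,620 case-by-band cells.
- Slides made: 180 x 8 = 1,440.
- Shortfall: 1,620 - 1,440 = 180, and 180 / 1,620 = 11.1%.
- Average per band: 1,440 / 9 = 160 over both systems, or 720 / 9 = 80 per system. With eight bands it would be 180 and 90.

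**Totals under each consistent reading.**

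| Reading | Prepared | Fillers | Ratio | Slides | Readings |
|---|---|---|---|---|---|
| As stated | 3,000 | 2,000 | 1.50:1 | 5,000 | 15,000 |
| Eight bands, fillers kept | 2,880 | 2,000 | 1.44:1 | 4,880 | 14,640 |
| Eight bands, 960 read as per system | 2,880 | 1,920 | 1.50:1 | 4,800 | 14,400 |
| Nine bands in one arm, fillers kept | 3,060 | 2,000 | 1.53:1 | 5,060 | 15,180 |

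The third row is the only recomputed one that gives exactly 3:2. It also fills 48 whole sets of 100.

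**Boundary.** A slide with exactly 1,600 abnormal cells belongs to both of the last two bands. No other boundary is shared.

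**The case against.** Several points against a harsher reading stand.

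- *The series cannot be made.* A reader might infer this, but the text speaks of establishing sets of slides and does not require every case to fill every band. Eight preparations per case can be spread over nine bands across 180 cases. What is missing is the rule for doing so.
- *Confounding is built in.* The document does not say that the omitted band follows the case. Two panel members count the abnormal cells on every slide, so the achieved number is known whatever the nominal band. The part 2 Statistical Analysis fits a random effects model with a source term and a covariate for diagnostic sub-type, and such a model tolerates cases that lack a band. Matching is incomplete, not destroyed, and the sample size does not rely on it.
- *The lowest bands are the ones lost.* Nothing in the text supports this. Mixing with negative material moves a case towards the low bands.
- *Power falls below plan.* The 90 slides per band and its power are stated for cellularity bands, and that series has eight. No power is claimed for the abnormal-cell bands, so an average of 80 breaches no stated requirement.
- *The totals may be rounded.* They are round numbers, and the assessments are called approximate. But 3,060 rounded to 3,000 would still contradict eight preparations and the 1,440 per system.

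The overlap at 1600 is trivial alone. A scanty case may also fail to reach a high band whether there are eight or nine, so the band count is not the only source of empty cells.

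**Conclusion.** The point holds as an inconsistency in the design text and in one slide total. Eight preparations do not match nine abnormal-cell bands. Each of the 180 cases in that series must miss at least one band (11% of case-by-band cells; on average 80 and not 90 slides per band per system, if cases are halved within system), and no rule governs which. Confounding of band with case type is a foreseeable risk, partly mitigated by the planned counts and model. It is not an established bias, and the power stated for the cellularity bands is not touched.

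The 3,000 prepared slides does not follow from the design. The sample size section points to 2,880. The alternative of 3,060 is nearer to 3,000, so the document does not settle whether eight or nine bands was intended. It should be corrected before slides are made, because an uneven allocation is hard to repair once residual material has been used.

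**What to change.** Make the number of abnormal-cell bands equal the number of preparations.

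1. **Simplest option, consistent with the sample size section.** Merge the top two bands into 800 or more. This gives eight bands and removes the overlap. The price is that there is no separate estimate above 1,600 abnormal cells.
2. **Rule for bands that cannot be filled.** Set in advance what happens when a case cannot reach a band, so that the choice is not left to how rich the case is. This is needed even after the merge, because a scanty case may still not reach 800.
3. **Totals.** Restate prepared slides as 2,880. Then reconcile the 2,000 fillers, 5,000 slides and about 15,000 readings in Design with the 960 in Sample Size. Keeping 2,000 fillers gives 4,880 slides and 14,640 readings. If 960 is meant per system, there are 1,920 fillers, 4,800 slides and 14,400 readings, at exactly 3:2. The per-system reading is an inference and should be stated if adopted. It also changes the explicit 1,000 negative plus 1,000 inadequate, so the sentence on 200 HPV-negative slides among the 1,000 negatives would need rewording.
4. **If nine bands are intended.** State nine preparations for that arm and 3,060 prepared slides, make the last two bands exclusive, and carry the change into Sample Size. With 2,000 fillers this gives 5,060 slides and 15,180 readings.

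Options 1 to 3 cost protocol wording, band labels in the database and a short allocation rule. Option 4 also costs 180 more prepared slides than 2,880, each with its panel counts and readings.
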